6.4. Handling of Dropouts or Missing Data

For the primary and key secondary efficacy endpoint analyses subject to type 1 error rate control, data for participants with missing values at the 72-week visit (or weight related measurements at

176-week visit for participants with prediabetes at randomization) will be imputed based on the method described in Section 6.13.1.3. However, for the parameters with only 1 postbaseline measure during the analysis period per schedule of activity, the last observation carried forward (LOCF) approach will be applied to impute the endpoint when ED measure is available.

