6.13. Efficacy Analyses

For submission of Study GPHK to the US FDA to support the registration of tirzepatide for chronic weight management, all primary and key secondary efficacy assessments will be guided by the “hybrid” estimand conducted using the FAS. Assessment of the primary and key secondary objectives (except for endpoint “delaying the onset of diabetes during 176 weeks or 193 weeks [for participants with prediabetes at randomization]”) will be conducted with multiple imputation of missing data (see Section 6.13.1.3).

For other regulatory agencies, publications and other purposes, the assessment of efficacy objectives will be guided by the “efficacy” estimand using the EAS.

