6.13.1.1. Analysis Related to the Efficacy Estimand

The analysis related to efficacy estimand will be conducted utilizing data in the EAS.

For the mean percent body weight change from randomization, a MMRM will be conducted. Restricted maximum likelihood (REML) will be used to obtain model parameter estimates and the Kenward-Roger option will be used to estimate the denominator degrees of freedom. The response variable of MMRM will be the percent change in body weight from baseline values obtained at each scheduled post baseline visit.

For the percentage of participants achieving at least 5% body weight reduction from randomization over time, a logistic regression model will be used with the response variable of the percentage of participants achieving at least 5% body weight reduction at each scheduled postbaseline visit.

For MMRM the independent variables of analysis model is treatment group, visit, treatment-by-visit interaction, stratification factors (prediabetes status at randomization, sex and country/pooled country) as fixed effects, and baseline body weight as a covariate. An unstructured covariance structure will model relationship of within-patient errors. If this model fails to converge, the following variance covariance structures will be tested in order until convergence is achieved:

- heterogeneous Toeplitz
- heterogeneous first order autoregressive
- heterogeneous compound symmetry
- Toeplitz
- first order autoregressive, and
- compound symmetry.

The first covariance structure that converges will be used.

With the aid of the MMRM analysis, 2-sided 95% CIs for mean percent change in body weight from randomization to the 72-week visit for tirzepatide 10 mg and 15 mg compared to placebo will be derived and summarized. The resulting least squares mean (LSM) estimates of mean percent change in body weight from baseline will be plotted by visit and by study treatment.

A logistic regression model with terms of treatment group, country/pooled country, sex, and prediabetes status at randomization as fixed effects, and baseline body weight as a covariate, will be conducted for percentage of participants achieving at least 5% body weight reduction from randomization at the 72 week visit. Missing body weight measurement at 72 week will be imputed by the predicted value from MMRM model aforementioned, then the continuous measurements will be dichotomized into status of achieving at least 5% body weight reduction

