(Yes or No). A logistic regression will be utilized to analyze proportion of participants with at least 5% body weight reduction at each nominal visit from randomization through 72 weeks.

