6.13.3.1. Other Secondary and Exploratory Efficacy Analyses

Unless otherwise specified, other secondary and exploratory efficacy analyses will be conducted using EAS. Missing data will be imputed using LOCF or handled through MMRM without utilizing multiple imputation technique.

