tirzepatide 5 mg QW (for participants with prediabetes at randomization) is superior to placebo at 176 weeks	Mean percent change in body weight from randomization	MMRM model in Section 6.13.1.1	Only for participants with prediabetes at randomization in the EAS. Model terms will include treatment group, visit, and treatment-by-visit interaction, country/pooled country, sex as fixed effects, and baseline body weight as a covariate.
tirzepatide 5 mg, 10 mg, and/or 15 mg QW is superior to placebo (for participants with prediabetes at randomization) at 176 weeks	Percentage of participants achieving $\geq 5\%$ body weight reduction from randomization	logistic model in Section 6.13.1.1	same as above
tirzepatide (all doses combined) is superior to placebo (for participants with prediabetes at randomization) at 176 weeks:	Mean change in SF-36v2 acute form physical functioning domain (PF) score from randomization	MMRM model in Section 6.13.1.1	same as above but using baseline SF-36 v2 acute PF score as a covariate.
	Mean change in IWQOL-Lite-CT Physical function composite (PF) score from randomization	MMRM model in Section 6.13.1.1	Similar to above but using baseline IWQOL-Lite-CT PF score as a covariate.

Abbreviations: ANCOVA = analysis of covariance; BMI = body mass index; DBP = diastolic blood pressure; HbA1c = hemoglobin A1c; IWQOL-Lite-CT = Impact of Weight on Quality of Life-Lite-Clinical Trials Version; LDL-C = low-density lipoprotein cholesterol; LOCF = last observation carried forward; LSM = least squares mean; MMRM = mixed model for repeated measures; QW = once-weekly; SF-36v2 = Short Form 36 version 2 Health Survey; VLDL-C = very low-density lipoprotein cholesterol.

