6.13.3.3. Exploratory Efficacy Analyses

Table GPHK.6.6. Exploratory Efficacy Analysis

Objective	Relative to the efficacy measure:	Analysis Conducted
compare tirzepatide 5 mg, 10 mg, and/or 15 mg with placebo at 72 weeks	Percentage of participants achieving $\geq 25\%$ body weight reduction from randomization	logistic model in Section 6.13.1.1
compare tirzepatide 5 mg, 10 mg, and/or 15 mg with placebo at 72 weeks	Percentage of participants whose BMI shifts between clinically relevant categories, i.e., from baseline (<25, 25 to <30, 30 to <35, 35 to <40, ≥ 40) to postbaseline (<25, 25 to <30, 30 to <35, 35 to <40, ≥ 40)	Shift analysis will be conducted based on data from EAS.

Exploratory Efficacy Analysis

Objective	Relative to the efficacy measure:	Analysis Conducted
compare tirzepatide 5 mg, 10 mg and/or 15 mg with placebo at 176 weeks	Same as above	Shift analysis will be conducted for the participants with prediabetes at randomization from EAS.
visualize tirzepatide 5 mg, 10 mg and/or 15 mg with placebo percent weight loss change from randomization up to safety follow-up after 72 weeks	Percent body weight loss measured at postbaseline from randomization to 72 weeks plus 4 weeks safety follow-up	Time-course plot will be generated. Only the participants who complete the 72 weeks treatment and have the safety follow-up (Visit 801) will be included.
compare tirzepatide QW (all dose combined) with placebo at 72 weeks	Percentage of participants change in glycemic category, that is, from baseline (normoglycemia, prediabetes, T2DM) to postbaseline (normoglycemia, prediabetes, T2DM)	Shift analysis will be conducted based on data from EAS.
compare tirzepatide QW (all dose combined) with placebo at 176 weeks	Same as above	Shift analysis will be conducted for the participants with prediabetes at randomization from EAS.

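### Efficacy estimand: missing Week 72 weights are replaced by a single MMRM prediction and then dichotomised, which biases the responder rates and odds ratios even under missing at random

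*SAP*

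**What the plan says.** SAP 6.13.1.1 analyses the efficacy estimand on the Efficacy Analysis Set, which drops data obtained more than 7 days after the last dose (SAP 6.1, Table GPHK.6.1). A weight retrieved at Visit 99 after early discontinuation is therefore generally missing here. For the ≥5% responder endpoint, "Missing body weight measurement at 72 week will be imputed by the predicted value from MMRM model aforementioned". The value is then dichotomised and a logistic model is fitted.

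The same model is used widely:
- at every visit: "A logistic regression will be utilized to analyze proportion of participants with at least 5% body weight reduction at each nominal visit";
- for the ≥10%, ≥15% and ≥20% key secondaries (Table GPHK.6.4);
- for ≥5% at Week 176 in Table GPHK.6.5, under the objective "tirzepatide 5 mg, 10 mg, and/or 15 mg QW is superior to placebo (for participants with prediabetes at randomization) at 176 weeks";
- for ≥25% in Table GPHK.6.6, which cites the "logistic model in Section 6.13.1.1";
- in the subgroup analyses of 6.16.1, which repeat the predicted-value rule.

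Multiple imputation is described only for the hybrid estimand. SAP 6.13 says in its FDA paragraph that the assessment "will be conducted with multiple imputation of missing data"; SAP 6.13.1.2 cites Rubin; SAP 6.13.1.3 opens by limiting itself to the hybrid estimand. SAP 6.4, however, says of all Type 1 error controlled Week 72 endpoints that missing values "will be imputed based on the method described in Section 6.13.1.3", naming no estimand. For other secondary and exploratory analyses, SAP 6.13.3.1 says: "Missing data will be imputed using LOCF or handled through MMRM without utilizing multiple imputation technique".

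The revision history (SAP section 3, item 7) shows the rule was introduced deliberately in version 2, following a cited methods paper.

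**The concern.** A predicted value is a conditional mean. It lacks the scatter that real Week 72 weights have around their prediction. Someone predicted just past the cut-off becomes a certain responder, and someone predicted just short of it a certain non-responder. A rate above 50% is pushed up and a rate below 50% is pushed down. The logistic model then treats the filled-in values as observed.

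The consequences reach well beyond one table: "For other regulatory agencies, publications and other purposes, the assessment of efficacy objectives will be guided by the" efficacy estimand. The responder half of the co-primary and three sets of key secondaries, as reported outside the FDA submission, depend on this rule. The SAP also leaves open whether the prediction uses the participant's own earlier visits or only the fixed effects.

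**Working it through.** **Inputs (Protocol 9.2).** 600 per arm; SD 10%; 25% dropout; mean difference 11 points; ≥5% rates of 25% (placebo) and 90% (tirzepatide); 49% three-year dropout. Not in the documents: ρ, the correlation between the predictor and Week 72 change. The assumed range is 0.5, 0.7, 0.85, 0.95.

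**The plan's own figure.** With 450 completers per arm, 11 / (10 × √(2/450)) = 16.5 standard errors, so the stated power above 90% is reproduced (about 100%). The two planning sets differ: with SD 10, rates of 25% and 90% imply a mean difference of 10 × (1.282 + 0.674) = 19.6 points, not 11. Both sets are shown.

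**Formula.** Let p be an arm's true responder rate and z = Φ⁻¹(p). The prediction has SD ρσ instead of σ, so a dropout counts as a responder with probability Φ(z/ρ) instead of p. With a fraction m missing at random, the arm's rate is

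(1 − m) × p + m × Φ(z/ρ).

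**Worked case, 25% vs 90%, ρ = 0.5, m = 0.25.** Placebo dropouts: Φ(−0.674/0.5) = 8.9%, so the arm rate is 0.75 × 25 + 0.25 × 8.9 = 21.0%. Tirzepatide dropouts: Φ(1.282/0.5) = 99.5%, so the arm rate is 0.75 × 90 + 0.25 × 99.5 = 92.4%. The difference is 71.4 points and the odds ratio 45.6.

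| Case (25% missing) | True | ρ=0.5 | ρ=0.7 | ρ=0.85 | ρ=0.95 |
|---|---|---|---|---|---|
| 25% vs 90%, ≥5%: difference | 65.0 | 71.4 | 68.7 | 66.8 | 65.6 |
| same: odds ratio | 27.0 | 45.6 | 36.9 | 31.3 | 28.3 |
| same: 95% CI coverage (simulated) | – | 17% | 55% | 83% | 94% |
| 11 points, ≥5%: difference | 41.5 | 49.0 | 45.1 | 43.1 | 42.0 |
| same: odds ratio | 5.9 | 8.8 | 7.2 | 6.4 | 6.1 |
| same: 95% CI coverage (simulated) | – | 21% | 69% | 90% | 94% |
| 11 points, ≥10%: difference | 35.0 | 37.1 | 36.5 | 35.8 | 35.3 |
| 11 points, ≥15%: difference | 23.6 | 20.8 | 22.6 | 23.3 | 23.5 |
| same: odds ratio | 8.0 | 8.8 | 9.2 | 8.8 | 8.3 |
| 11 points, ≥20%: difference | 12.6 | 9.9 | 11.0 | 11.9 | 12.4 |
| same: odds ratio | 10.9 | 11.0 | 12.0 | 12.1 | 11.4 |

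Coverage is for the unadjusted interval, 600 per arm, 1,500 runs. Multiple imputation in the same simulations gave the true values with 95–99% coverage.

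**Covariate-adjusted model.** With one covariate assumed to explain 5% of variance and rates of 25% vs 90%, the true adjusted odds ratio of 29.9 became 51.6, 41.8, 35.3 and 32.2 across the four ρ.

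**Dropout timing.** This used the protocol's weighing visits and an assumed correlation with Week 72 of (week/72)^0.25 to ^0.5. At 11 points, ≥5% (true 41.5), the rule gives 44.7–47.1 if dropout is even over 72 weeks, 46.6–49.9 if 60% of dropouts were last weighed by Week 16, and 42.2–42.9 if all were last weighed at Week 48 or 60.

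**Separate check under dropout depending on observed weight.** In a simulation on the protocol's visits with rates of 25% and 90% (true odds ratio about 27), the conditional mean gave 44.8, 33.0 and 28.9 at mean R² (that is, ρ²) of 0.33, 0.67 and 0.87. Residual draws on the same data gave 26.8–27.2.

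**Fixed-effects reading.** If the prediction ignores earlier visits, nearly every dropout falls on the arm mean's side: 0.75 × 25 = 18.8% and 0.75 × 90 + 25 = 92.5%, odds ratio 53.4.

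**Week 176.** If the rates there were those of the 11-point case (an assumption) with 49% missing, the true 41.5 becomes 56.1, 48.6, 44.6 and 42.4.

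**No true effect.** The ≥5% test alone, at nominal 5% and a 25% rate, rejects in 7.4, 7.1, 6.1 and 5.4% of runs. The joint co-primary test at 2.5% rejects in 1.1, 1.3, 1.0 and 0.8%; with both means exactly on the cut-off the highest figure is 2.3%.

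**The case against.** The SAP never says that one value only is imputed, and the rule follows a cited paper that is not in the documents; the wording may be shorthand for a procedure with draws. That possibility stands. But 6.13.1.1 would then omit the number of draws, the combining rule and the conditioning, while the SAP does name multiple imputation where the hybrid estimand needs it. A programmer following the text would impute once.

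The size rests on an assumed ρ, and the poorest coverage belongs to ρ = 0.5. This also stands. At ρ = 0.95 the ≥5% shift is about half a point and coverage is 94%; late dropouts cause little bias. Early discontinuers are the ones whose Week 72 weight is least predictable.

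The direction is not universal. If both arms exceed 50%, the difference can shrink: 70% vs 95% goes from 25.0 to 22.4 points at ρ = 0.5. That requires a placebo rate far above the planned 25%, and the odds ratio still rises there (8.1 to 9.1). At ≥15% and ≥20% under 11 points, the difference shrinks while the odds ratio rises, so direction depends on the scale.

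SAP 6.4 and 6.13.3.1 can be read consistently with 6.13.1.1: the first points to a section limited to the hybrid estimand, and the second yields where something else is specified. The edits proposed to them are clarifications.

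**Conclusion.** The concern holds and should be fixed. As written, the rule gives biased responder estimates under the very assumptions that justify the MMRM. At the planned placebo rate of 25%, the ≥5% effect is inflated: under random dropout by 0.6 to 6.4 points for 25% vs 90%, and by 0.5 to 7.5 points for an 11-point difference, across ρ from 0.95 to 0.5. Odds-ratio bias falls to about 5% only when R² reaches about 0.9 with 25% missing. These sizes assume normally distributed percent change and the stated ρ; the documents give neither ρ nor dropout timing.

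The MMRM mean-change co-primary, the joint co-primary error rate, the superiority conclusion at planned effects and the FDA hybrid analysis are not threatened. The issue is the accuracy of the reported percentages, odds ratios and intervals.

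**What to change.** - In SAP 6.13.1.1 and 6.16.1, replace the predicted value by multiple draws (state the number, for example 100) from the MMRM predictive distribution. Include parameter uncertainty and residual error, and condition on the participant's earlier on-treatment visits, under missing at random on the Efficacy Analysis Set.
- Dichotomise each completed data set, fit the stated logistic model, and combine the log odds ratios by Rubin's rules.
- Apply this wherever the responder model is used: each nominal visit, Week 176, and Tables GPHK.6.4 to 6.6.
- In 6.13.3.1, except these analyses from the exclusion of multiple imputation. In 6.4, state that 6.13.1.3 serves the hybrid estimand and 6.13.1.1 the efficacy estimand.
- If draws are already intended, 6.13.1.1 must say so, with their number, the conditioning and the combining rule.

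The cost is wording in four SAP sections and modest programming; no new data are needed. The ≥5% results, and usually the ≥10% results, become slightly less favourable. Differences at ≥15% and ≥20% may move slightly either way.

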6.13.1.2. Analysis Related to the Hybrid Estimand

The analysis related to “hybrid” estimand will be conducted using data in the FAS.

The analysis for the mean percent change in body weight will be conducted utilizing ANCOVA. The response variable for the ANCOVA model will be percent change in body weight from randomization at 72 weeks. A logistic regression model will be used for the analysis of the percentage of participants achieving at least 5% body weight reduction obtained at the 72-week visit. Both models will include terms of treatment group, country/pooled country, sex, and prediabetes status at randomization as fixed effects and baseline body weight as a covariate. The ANCOVA analysis will be conducted with multiple imputation of missing body weight at 72 weeks (see Section 6.13.1.3 for details) and statistical inference over multiple imputation of missing data guided by Rubin (1987). As for the logistic regression, missing body weight data at 72 weeks will be imputed first based on Section 6.13.1.3, then the continuous measurements will be categorized into status of achieving at least 5% body weight reduction (Yes or No).

With the aid of the ANCOVA model, 2-sided 95% CI for mean change in percent body weight from baseline to the 72-week visit between tirzepatide 10 mg and placebo, as well as tirzepatide 15 mg and placebo will be derived.

With the aid of the logistic regression model, 2-sided 95% CI and odds ratio for percentage of participants achieving at least 5% body weight reduction from baseline to the 72-week visit between tirzepatide 10 mg and placebo, as well as tirzepatide 15 mg and placebo will be derived.

6.13.1.3. Methods for Imputations

For efficacy analyses relative to “hybrid” estimand, the intercurrent events (ICEs) and the resulting missing values will be handled as follows:

- Category 1: for missing data solely due to exceptional circumstances, such as pandemic or natural disasters (after other reasons for missing data are ruled out), the analysis will consider the missing data as missing at random. The missing data will be imputed using all non-missing data of the primary outcome measurement from the same treatment arm.
- Category 2: for missing data due to all other ICEs: missing data will be imputed based on retrieved dropouts in the same treatment arm, defined as observed primary outcome measurements, from participants in the same treatment group, who had their efficacy assessed after early discontinuation of the study drug. In case where there are not enough retrieved dropouts to provide a reliable imputation model (for example, the model implemented by the SAS program does not converge), an alternative multiple imputation method with reference to the placebo group (that is, placebo multiple imputation) will be used.

6.13.1.4. Sensitivity Analysis Related to the Hybrid Estimand

For submission of Study GPHK to the US FDA to support the registration of tirzepatide for chronic weight management, additional sensitivity analyses of the primary efficacy outcomes will be conducted using the FAS and guided by the “treatment-regimen estimand, which represents the efficacy irrespective of adherence to study drug. This assessment will analyze percent change in body weight obtained at the 72-week visit using an ANCOVA and the percentage of participants achieving at least 5% body weight reduction obtained at the 72-week visit using a logistic regression model. The terms for both models will be the same as specified in Section 6.13.1.2 for “hybrid” estimand.

Missing values of change in body weight at the 72-week visit will be imputed based on observed body weight change from baseline values at the visit from participants in the same treatment group who had their efficacy assessed after early discontinuation of study drug. In cases where there are not enough retrieved dropouts to provide a reliable imputation model (for example, the model implemented by the SAS program does not converge), an alternative multiple imputation method with reference to the placebo group (placebo multiple imputation) will be used. Analysis will be conducted with multiple imputations.

6.13.2. Secondary Efficacy Analyses Subject to Type 1 Error Rate Control

Table GPHK.6.4. Secondary Measures Controlled for Type 1 Error

Objectives	Relative to the efficacy measure:	Analysis conducted in a manner similar to	Additional Information
Tirzepatide 10 mg and 15 mg combined is superior to placebo:	Mean change in body weight (kg) from randomization at 20 weeks	MMRM model in Section 6.13.1.1 for efficacy estimand and ANCOVA model in Section 6.13.1.2 for hybrid estimand	
Tirzepatide 5 mg is superior to placebo:	Mean percent change in body weight from randomization and percentage of participants achieving at least 5% body weight reduction at 72 weeks	Section 6.13.1.1 for efficacy estimand and Section 6.13.1.2 for hybrid estimand	
Tirzepatide 10 mg and/or 15 mg is superior to placebo:	Percentage of participants achieving body weight reduction $\geq 10\%$, $\geq 15\%$ and $\geq 20\%$ at 72 weeks	logistic model in Section 6.13.1.1 for efficacy estimand and logistic model in Section 6.13.1.2 for hybrid estimand	
	Mean change in waist circumference (cm) from randomization at 72 weeks	MMRM model in Section 6.13.1.1 for efficacy estimand and ANCOVA model in Section 6.13.1.2 for hybrid estimand	LSM estimates will be plotted by treatment through 72-weeks.

Secondary Measures Controlled for Type 1 Error

Objectives	Relative to the efficacy measure:	Analysis conducted in a manner similar to	Additional Information
Tirzepatide 10 mg and 15 mg combined is superior to placebo	Mean change in SF-36 v2 acute form Physical Functioning domain score from randomization at 72 weeks	ANCOVA model with the terms of treatment group, stratification factors as fixed effects, and baseline SF-36 v2 acute form Physical Functioning domain score as a covariate.	For efficacy estimand, missing data will be imputed based on LOCF method. For hybrid estimand, missing data will be imputed based on Section 6.13.1.3.
Tirzepatide (all doses combined) is superior to placebo:	Mean change in triglycerides, HDL-C, non-HDL-C, SBP and fasting insulin from randomization at 72 weeks	MMRM model in Section 6.13.1.1 for efficacy estimand and ANCOVA model in Section 6.13.1.2 for hybrid estimand	For hybrid estimand, missing data will be imputed first for each treatment based on Section 6.13.1.3, then combine all tirzepatide doses.
Tirzepatide 10 mg, and/or 15 mg is superior to placebo:	Mean percent change in body weight from randomization at 176 weeks (for participants with prediabetes at randomization)	MMRM model in Section 6.13.1.1 for efficacy estimand and ANCOVA model in Section 6.13.1.2 for hybrid estimand. Include country, sex as stratification factors in each model.	Only for participants with prediabetes at baseline. For the hybrid estimand, missing data at 176 week will be imputed based on Section 6.13.1.3,
Tirzepatide (all doses combined) is superior to placebo:	Time to onset of T2DM during 176 weeks (or during 193 weeks) for participants with prediabetes at randomization	Cox-proportional hazards model will be used with the terms of treatment group (all tirzepatide doses combined and placebo), country and sex as fixed effects, and baseline fasting glucose value as a covariate.	Only for participants with prediabetes at baseline.

Abbreviations: ANCOVA = analysis of covariance; HDL-C = high-density lipoprotein cholesterol; LOCF = last observation carried forward; LSM = least squares mean; MMRM = mixed model for repeated measures; SBP = systolic blood pressure; SF-36 = Short Form -36 version 2 Health Survey; T2DM = type 2 diabetes mellitus.

Decision will be guided by the 2-sided p-values in each objective, and details will be included in Section 6.13.3.

6.13.3. Type 1 Error Rate Control Strategy for Primary and Key Secondary Efficacy Analyses

No type 1 error rate adjustments will be made for conducting analyses relative to “efficacy” estimand and “hybrid” estimand, as these two estimands are intended for different purposes. For analysis within each estimand, type 1 error rate control strategy for evaluation of primary and key secondary objectives is illustrated in Figure GPHK.6.1. The hypotheses for the primary and key secondary objectives are as follows:

- $H_{15,1}$ and $H_{10,1}$: superiority of tirzepatide 10 mg and/or 15 mg versus placebo for percent change in body weight from randomization and percentage of participants who achieve $\geq 5\%$ body weight reduction at 72 weeks
- $H_{15,2}$ and $H_{10,2}$: superiority of tirzepatide 10 mg and/or 15 mg versus placebo for percentage of participants who achieve $\geq 10\%$ body weight reduction from randomization at 72 weeks
- $H_{15,3}$ and $H_{10,3}$: superiority of tirzepatide 10 mg and/or 15 mg versus placebo for percentage of participants who achieve $\geq 15\%$ body weight reduction from randomization at 72 weeks
- $H_{15,4}$ and $H_{10,4}$: superiority of tirzepatide 10 mg and/or 15 mg versus placebo for percentage of participants who achieve $\geq 20\%$ body weight reduction from randomization at 72 weeks
- $H_{15,5}$ and $H_{10,5}$: superiority of tirzepatide 10 mg and/or 15 mg versus placebo for change from randomization in waist circumference (cm) at 72 weeks
- $H_{1015,6}$: superiority of pooled tirzepatide 10 mg and 15 mg versus placebo for change in body weight (kg) from randomization at 20 weeks
- $H_{5,1}$: superiority of tirzepatide 5 mg versus placebo for percent change in body weight from randomization **and** percentage of participants who achieve $\geq 5\%$ body weight reduction at 72 weeks
- $H_{p,7}$: superiority of tirzepatide (all doses combined) versus placebo for change in systolic blood pressure (SBP) (mmHg) from randomization at 72 weeks
- $H_{p,8}$: superiority of tirzepatide (all doses combined) versus placebo for change in triglycerides (mg/dL) from randomization at 72 weeks
- $H_{p,9}$: superiority of tirzepatide (all doses combined) versus placebo for change in - non-high-density lipoprotein cholesterol (non-HDL-cholesterol) (mg/dL) from randomization at 72 weeks
- $H_{p,10}$: superiority of tirzepatide (all doses combined) versus placebo for change in high-density lipoprotein cholesterol (HDL-cholesterol) (mg/dL) from randomization at 72 weeks
- $H_{p,11}$: superiority of tirzepatide (all doses combined) versus placebo for change in fasting insulin (pmol/L) from randomization at 72 weeks
- $H_{1015,12}$: superiority of pooled tirzepatide 10 mg and 15 mg versus placebo for change in SF-36v2 acute form Physical Functioning domain score from randomization at 72 weeks.
- $H_{15,13}$ and $H_{10,13}$: superiority of tirzepatide 10 mg and/or 15 mg versus placebo for change in percent body weight from randomization at 176 weeks (for participants with prediabetes at randomization).
- $H_{p,14}$ and $H_{p,15}$: superiority of tirzepatide (all doses combined) versus placebo for delaying the onset of type 2 diabetes mellitus (T2DM) during 176 weeks or 193 weeks (for participants with prediabetes at randomization).

[figure not shown]

Figure GPHK.6.1. Type 1 error control strategy for primary and key secondary efficacy endpoints.

Abbreviations: HDL-C = high-density lipoprotein cholesterol; SBP = systolic blood pressure; SF-36v2 PF = Short Form survey-36 version 2 physical functioning; T2DM = type 2 diabetes mellitus; p = tirzepatide all doses combined; PWL = percent weight loss WC = waist circumference; wk = week, WT = weight loss in kg

